**Summary of Changes from Previous Version:**  
*See section 10.4 for detailed description*

Affected Section(s)	Summary of Revisions Made	Rationale	Date of Revision
Throughout Protocol	Remote consent procedure (telephone, email, or mail)	Re-opening of study after COVID crisis to accommodate social distancing	6/9/20
5.1	Inclusion Criteria (10) to include "or Spanish – Bronx, NY site)	Grammatical error	6/10/20
9.4.2	Analysis of the Primary Endpoints – ED Visit and Hospitalization Count language revision	Biostats review deemed revisions	6/10/20
9.4.3	Analysis of Secondary Endpoints & Feasibility Outcomes language revisions	Biostats review deemed revisions	6/10/20
9.4.5	Baseline Descriptive Statistics language revision	Biostats review deemed revisions	6/10/20
Throughout Protocol	Primary endpoint follow-up period from 18 months to 9 months (12 months observational)	Timeline revision due to COVID pandemic	4/30/21
6.1	Assignment of 3 mentees per mentor revised to 4 mentees	Mentee assignment revisions to meet timeline goals	4/30/21
7.2	T2 surveys administered at time of discontinuation	Established assigned discontinuation surveys	4/30/21

## STATEMENT OF COMPLIANCE

The trial will be conducted in accordance with International Council on Harmonisation Good Clinical Practice (ICH GCP), applicable United States (US) Code of Federal Regulations (CFR), and the NIDDK Terms and Conditions of Award. The Principal Investigator will assure that no deviation from, or changes to the protocol will take place without prior agreement from the funding agency and documented approval from the Institutional Review Board (IRB), except where necessary to eliminate an immediate hazard(s) to the trial participants. All personnel involved in the conduct of this study have completed Human Subjects Protection and ICH GCP Training.

The protocol, informed consent form(s), recruitment materials, and all participant materials will be submitted to the IRB for review and approval. Approval of both the protocol and the consent form(s) must be obtained before any participant is consented. Any amendment to the protocol will require review and approval by the IRB before the changes are implemented to the study. All changes to the consent form(s) will be IRB approved; a determination will be made regarding whether a new consent needs to be obtained from participants who provided consent, using a previously approved consent form.

Peer mentorship to improve outcomes in patients on maintenance hemodialysis (PEER-HD) Version 3.0  
Protocol 2018-01  
30 April 2021

## 1 PROTOCOL SUMMARY

### 1.1 SYNOPSIS

**Title:** Peer Mentorship to improve outcomes in patients on maintenance hemodialysis

**Short Title:** PEER-HD

**Grant Number:** R18DK118471

**Study Description:** Pragmatic trial to test the effects and implementation of a low cost, educational, telephone-based, peer-mentor intervention on ED visits and hospitalizations among high-risk patients receiving hemodialysis.

**Objectives:**

Primary Objectives:

- 1) To perform a randomized controlled trial to evaluate the effects of a 3-month peer mentor intervention on a composite of ED visits and hospitalizations in patients on hemodialysis compared to usual care.
- 2) To test the feasibility of a dialysis peer training program.

Secondary Objective:

To evaluate the effect of peer mentoring intervention on dialysis adherence behaviors, dialysis knowledge, self-efficacy and perception of social support in intervention compared to control participants.

**Endpoints:**

Primary Endpoint: Composite count of ED visits and hospitalizations during 3 months of intervention and 15 months of follow up (18 months observation).

Due to the covid pandemic and recommendations from the DSMB, after 4/30 all participants' post-activity period follow up will be limited to 9 months (12 months of observation), or truncated to the current observation period total of between 12 and 18 months.

Secondary Endpoints:

- 1) Dialysis treatment adherence – mean missed minutes per month
- 2) Mean monthly inter-dialytic weight gain (%), serum albumin (g/dL);
- 3) Perceived self-efficacy, knowledge, perception of social support and quality of life.

Feasibility Endpoints (intervention only):

- 1) number of telephone contacts per week;
- 2) content of telephone conversations;

Feasibility of Peer Mentor Training:

- 1) attendance records for all sessions
- 2) change in pre-/post-knowledge assessments after training
- 3) content & descriptive evaluation of course evaluations

Peer mentorship to improve outcomes in patients on maintenance hemodialysis (PEER-HD) Version 3.0  
Protocol 2018-01  
30 April 2021

**Study Population:** 20 Mentor adult in-center hemodialysis patient participants  
200 Adult in-center hemodialysis patient participants  
Enrolled from dialysis units in or near the Bronx, NY and Nashville, TN

**Trial Type:** Pragmatic Randomized Trial

**Description of Sites/Facilities Enrolling Participants:** Participants are enrolled from multiple dialysis units affiliated with Albert Einstein (AECOM) College of Medicine and Vanderbilt University Medical Center (VUMC). AECOM will serve as the coordinating center.

**Description of Study Intervention:** Intervention will have 2 phases:  
1) **Mentor training**

- 4 Training sessions, 2 hours each covering topics in dialysis care, coaching and motivational interviewing techniques.
- Refresher 2-hour session at 3-months and 10-months
- Financial compensation by hour for training
- Assessments of skills, role modeling & simulations, exit interviews

2) **Telephone based 3-month intervention** by mentors for mentees

- Weekly phone contact with mentee (1-3 mentees per mentor)
- Social mixers at the dialysis facility, or other group activities

**Usual care control group patient participants**

- Usual care as per facility procedures and protocols

All participants:  
Provision of written educational material

**Study Duration:** 48 months

**Participant Duration:** Mentors: up to 30 months  
Intervention or Control group participants: 12 to 18 months

**Study Oversight:** National Institute of Diabetes and Digestive and Kidney Diseases /  
National Institutes of Health  
Project Scientist: [name]  
Address: [name]  
[name]  
[name]  
[contact]  
Email: [contact]

**Data Safety & Monitoring Board:** Members [REDACTED]

[figure not shown]

### 1.2 SCHEMA

**Figure 1. Mentors N~20**

**Figure 2. Patient Participants N=200 [All sites; Estimated enrollment AECOM=140; VUMC=60]**

At the final study visit, all mentors and those randomized to the peer mentoring intervention will complete program evaluation interviews and surveys to gain feedback on the intervention.

Due to impact of the covid pandemic, the study DSMB recommended prioritizing enrollment and reduction of follow-up observational time. The recommendation is to limit total observation time to 12-months for intervention and control participants. Participants currently enrolled and who have passed the 12-month point will execute their T2 visit as soon as possible and truncate observation (13-18 months). For those whose observation time is less than 12-months, or any new enrolled participants, the T2 assessment will be moved to the 12-month time point. Mentors, may complete T2 at 18-months (Einstein site), or may complete T2 visit at 12-months if all other mentor activities have been completed at the site. Medical record monthly review will only occur for the observation period and will also be truncated at the time of the T2 visit. This alteration of the study design was approved by the DSMB and also the NIH program officer.

### 1.3 SCHEDULE OF ACTIVITIES

Table 1. Mentor and Patient participant study activities

Mentors		Pre-screening (Pre-consent)	Visit 1 – Day 1	Training 1-4; Within 6-8 Weeks after V#1	Each Month	~Month 3, Month 10, as needed	Visit 2-Month 9 ± 30d	Visit 3-Mon 18 ± 30d; between 12-18M or at 12M depending on date	Final visit Month 18 ± 30d between 12-18M or at 12M depending on date
Review Eligibility		x							
Informed Consent			x						
Demographics			x						
Clinical history			x						
Baseline assessments			x						
Mentors (continued)									
Post training assessments (knowledge/formative/summative)			x						
Coordinator survey/check-in				x					
EMR Data Abstraction & Review				x					
Peer Mentor Refresher course (as needed)					x				
Optional social mixer or other group activity					x				
9-month follow-up assessments						x			
18-months follow up assessments							x		
Program evaluation interviews & field notes								x	

Time of the start of the intervention activity with the first mentee will determine the start of when subsequent study visits (9-month; 18-month, or between 12-18-months) will occur for mentors.

Intervention or Control Participants		Pre-screening	Visit 1	Each Month	Every 3-4 Months, as needed	Visit 2 Month 3 ± 30d	Visit 3 Month 18 ± 30d between 12-18M or at 12M depending on date	Final visit Month 18 ± 30d between 12-18M or at 12M depending on date
Review Eligibility		x						
Informed Consent			x					
Demographics			x					
Clinical history			x					

Baseline assessment surveys	x				
Kidney Disease Educational Materials	x				
Coordinator survey/check-in		x			
EMR Data Abstraction & Review		x			
3-month follow-up assessments				x	
18-month follow-up assessments, or between 12-18-months as noted depending upon enrollment date					x
Optional social mixer or group activity (intervention)			x		
Program evaluation interviews & field notes					x

Usual care group start time will begin at the time they receive the study kidney disease educational materials. Mentee group start time will begin at the time they receive their study phone and they are activated with their mentor.

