#### **Mentee Telephone PEER Support Program group**

The mentor telephone PEER support intervention includes a trained mentor, who is assigned 1-4 mentees. The mentees each will participate in telephone support for a 3-month period. Study telephones will be assigned to mentors and required to be used for all study activities and offered to mentees for use during the program. Intervention mentees will be offered a study supplied phone, or

permitted to use their own device with the understanding they will be responsible for any incurred costs on their own device.

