#### *Mentor telephone support*

Mentors are expected to call each mentee once a week, with a goal of talking for an average of 20 minutes. Call durations of at least 3 minutes will be considered complete. Mentors are asked to make a minimum of four attempts to reach mentees by phone on different days and times throughout the week. Both mentors and mentees are offered compensation based on the time executed for study calls. Mentors and mentees are asked to record in a log a record of their calls including notes on discussions. Mentors will also be given a study digital recorder. They are expected to randomly record calls with mentees for fidelity and content review, approximate 3-4 over the intervention period for each mentee. Mentor and mentees are informed that telephone billing records will be reviewed for characterization of attempts and contacts between mentors and mentees. Communication between mentors and mentees after conclusion of the 3-month period is not expected but will be permitted. Mentors will continue to use their assigned study phone for all calls.

Optional social mixers, or other similar group gathering (in-person or virtual) will be offered for all mentor and mentee participants. This will provide an opportunity for mentors and mentees to provide informal feedback to each other, as well as an opportunity for informal interactions with the study team. A study newsletter for mentors to share knowledge and encourage retention may be used.

The frequency and the mean duration will be measured, the content of the call recorded in a notebook by each member of the team after contact. During mentor training, a schedule of suggested themes and discussion content for calls will be provided. In general, the focus of the first 4 weekly calls will be to increase knowledge of the mentee, and the last 8 weekly calls will focus on motivational interviewing, emotional and affirmation support. The structure will be flexible to the needs of individual mentees.

If one member of the pair dies, then the study team will meet with the other member, provide counseling, engage the clinical provider, and offer being paired with another mentor/mentee.

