#### *Mentor PEER Phone Support*

Mentors will contact their mentees at least once a week for a total of 12 weeks. The mentees will also be given the option to contact their mentees should the need arise at any point during the 3-month intervention. Phone billing records will be reviewed to determine the total dose of intervention (call minutes with mentor) total for the period, monthly average, and weekly average. The distribution of the range of call duration for each mentee will also be described. A minimum of 3 minutes completed is required to count as a completed call.

Additional in-person, or video interactions between mentors and mentees will be self-reported by mentors in their contact logs, or as observed by study team during social mixers. These interactions will be included in the dose calculation of the intervention.

The quality of the mentor/mentee interactions will be evaluated using content analysis of recordings and the contact logs of mentors and mentees. Additional information of the quality will be evaluated by the study coordinator in the monthly or quarterly surveys of mentors and mentees.

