#### 9.4.3 ANALYSIS OF THE SECONDARY ENDPOINT(S)

The primary evaluation will be at the end of the study period (12 to 18-months) using all available data regardless of the period end for participants, and comparisons at 3M will be secondary. For the primary evaluation, we will test the longitudinal effect of a peer mentor led telephone intervention on mentee self-management skills including 1) dialysis adherence (mean number of outpatient dialysis hours per month), 2) mean monthly inter-dialytic weight gain (IDWG), and 3) mean monthly albumin levels. We

will compare the rate of change over time of the monthly secondary endpoints between two intervention groups using linear mixed effects regression model. In the regression model, the secondary endpoint (e.g. monthly mean dialysis hours) is the outcome variable with two main effects (the intervention assignment and months from baseline) and the interaction term between the main effects. The interaction term (i.e. the difference in slopes between two groups) is the primary predictor of interest. There will be three random intercepts to account for mentor effect, facility effect (out of seven facilities) and subject effect (to account for within correlation from repeated measurements). We will evaluate differences in baseline variables identified in Table 6 and if they are different between the groups, we will adjust for them as confounders.

For the secondary evaluation at 3M, we will perform Wilcoxon rank-sum test to compare the 3-months change of secondary endpoints between the intervention mentee and control mentees. To account for confounders, we will also fit linear regression model with two random intercepts. In the regression model, the 3 months-change of secondary endpoint is the outcome variable and the intervention assignment of the mentees is the primary binary predictor. The random intercepts will account for the correlation between mentees who share a common mentor as well as the correlation between mentees who are from a common dialysis facility.

Below, each endpoint is described including its source, scoring and planned analysis approach. Additional details for scoring of surveys is provided in the PEER HD Survey Scoring guide document. Within group (mentors) for change in outcomes over time will also be evaluated.

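### The 3-month visit window opens before the 12 weekly calls are finished, so some 3-month surveys can be taken with one to four planned calls still to come

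*Combined protocol and SAP*

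**What the plan says.** The schedule of activities (Section 1.3) places the second visit of intervention and control participants at "Visit 2 Month 3 ± 30d". For the intervention arm, time zero is the start of the intervention: "Mentee group start time will begin at the time they receive their study phone and they are activated with their mentor". For controls, "Usual care group start time will begin at the time they receive the study kidney disease educational materials".

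Section 6.1.1 gives the length of the program: "The mentees each will participate in telephone support for a 3-month period". Section 6.1.2 gives the schedule: "Mentors will contact their mentees at least once a week for a total of 12 weeks". Section 6.1.1 also describes the general content. At first, "the focus of the first 4 weekly calls will be to increase knowledge of the mentee"; after that, "the last 8 weekly calls will focus on motivational interviewing, emotional and affirmation support".

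Section 8.1 collects the surveys at baseline, 3 months and 12 to 18 months. They cover quality of life, self-efficacy, social support, coping, knowledge and communication, among others. Two mentee-only instruments, the Health Care Climate Questionnaire and the checklist on which mentees assess mentors, are listed at the 3-month visit only.

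For the analysis at 3 months, Section 9.4.3 states: "we will perform Wilcoxon rank-sum test to compare the 3-months change of secondary endpoints". It adds a mixed model for the same change and ranks the 3-month comparisons below those at 12 to 18 months. Section 4.3 describes the visit as the assessment at 3 months of intervention.

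**The concern.** The window is symmetric around month 3, but the intervention ends about a week before month 3. The early side of the window therefore overlaps the last weeks of calls. No section says that the visit must follow the last call, and the 3-month analysis has no term for visit timing or for calls received by then.

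Three things are at stake:

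- **Dilution of the survey contrast.** The calls outstanding at an early visit all fall in the later block, whose general focus is motivation and support. Self-efficacy and perceived social support are close to that content. Controls have nothing outstanding, so an early visit can only reduce what the intervention arm has received.
- **Mentor ratings.** The mentee-only instruments can be completed while mentoring is still under way.
- **No second chance near the end of the calls.** The next survey is at 12 to 18 months, so Visit 2 is the only survey close to the end of the intervention.

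**Working it through.** **Inputs.** Visit window: month 3 minus 30 to plus 30 days (Section 1.3). Time zero for mentees: activation with the mentor (Section 1.3). Calls: weekly for 12 weeks (Section 6.1.2), with an average goal of 20 minutes (Section 6.1.1). The documents do not define month 3 in days, so 91 is used here and 84 and 90 are shown for range.

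**1. The plan's own call count.** First 4 + last 8 = 12 calls, which agrees with weekly calls for 12 weeks. The end of week 12 is 12 × 7 = day 84.

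**2. The window.** It opens on day 91 − 30 = 61 (61/7 = 8.7 weeks) and closes on day 91 + 30 = 121, which is 61 days counted inclusively. Days 61 to 83 come before day 84: 23 days, and 23/61 = 38% of the window. The close is 121 − 84 = 37 days, or 5.3 weeks, after the end of week 12.

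**3. Calls outstanding by visit day.** Calls outstanding = 12 − completed weeks.

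| Visit day | Days | Outstanding | Days × outstanding |
|---|---|---|---|
| 61–62 | 2 | 4 | 8 |
| 63–69 | 7 | 3 | 21 |
| 70–76 | 7 | 2 | 14 |
| 77–83 | 7 | 1 | 7 |
| 84–121 | 38 | 0 | 0 |
| Total | 61 | | 50 |

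**4. Average shortfall if visits are spread evenly over the window (assumption).** 50/61 = 0.82 calls. That is 0.82/12 = 7% of all planned calls, 0.82/8 = 10% of the later block, and 0.82 × 20 = 16 of 240 goal minutes.

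If a call is instead counted once its week has started, days 61–63 have 3 outstanding, days 64–70 have 2 and days 71–77 have 1. The sum is 9 + 14 + 7 = 30, and 30/61 = 0.49 calls: 4% of 12, or 6% of 8.

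**5. Sensitivity to the length of month 3 (completed weeks, even spread).**

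- Month 3 = 90 days: the window is days 60–120. Days 60–62 have 4 outstanding, so the sum is 12 + 21 + 14 + 7 = 54, and 54/61 = 0.89 calls (7%).
- Month 3 = 84 days: the window is days 54–114. Days 54–55 have 5 outstanding and days 56–62 have 4, so the sum is 10 + 28 + 21 + 14 + 7 = 80, and 80/61 = 1.31 calls (11%).

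**6. Bounds for month 3 = day 91.** If every visit fell on day 61, 4 of 12 calls (33%) would be outstanding. If every visit fell on or after day 84, none would be. The even-spread figure lies between these, nearer the lower end.

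**7. Which outcomes depend on the visit date.** Missed minutes, interdialytic weight gain, albumin, ED visits and hospitalizations come from monthly record review (Section 8.1); monthly self-report also contributes to the ED visit and hospitalization counts (Sections 8.1 and 9.4.2). None of these is tied to Visit 2. Only the surveys and the mentor ratings are.

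**The case against.** The strongest case against the point is about size.

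- **The extreme is rare in the calendar.** A reader might infer that the 3-month surveys are taken with a third of the intervention undelivered, or that they would show only half of the full effect. Four outstanding calls apply to 2 of 61 days, and the documents give no visit dates. A loss of that size for the arm as a whole is not supported.
- **The comparison is secondary.** Section 9.4.3 puts the end-of-study evaluation first, and the primary endpoint does not use Visit 2.
- **Call content is flexible.** Section 6.1.1 gives the two blocks as a general pattern that adapts to the mentee, calls are at least weekly, and contact after 3 months is permitted. The count of support calls done by a given day is illustrative.
- **Dose is already recorded.** Section 8.1 takes the date and duration of every call from billing records, Section 6.4 allows a dose adjustment, and Section 9.4.9 examines dose.
- **Mentor ratings have company.** The questionnaire is reported descriptively (Section 9.4.3). Mentees are also surveyed monthly about the calls (Section 6.4), and intervention participants complete a program evaluation at the final visit (Section 1.2).
- **The late side matters too.** Surveys taken about five weeks after the last planned call could miss an effect that fades.
- **Wide windows help retention** in a pragmatic trial.

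All of this limits the point, and most of it stands. It does not remove the point. The plan permits surveys before the calls end, and neither of the 3-month analyses in Section 9.4.3 accounts for it. Billing dates make a check possible, but no such check is planned: Section 6.1.2 totals the dose over the whole period, so for an early visit the total includes minutes delivered after the outcome was measured.

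**Conclusion.** The point holds as a modest timing mismatch. With month 3 as day 91, a visit within window can precede the last one to four planned calls on 23 of its 61 days. The average shortfall is about 0.8 calls, or 7% of 12, if visits are evenly spread, and 0.5 to 1.3 calls (4% to 11%) across the counting rules and month lengths shown. If benefit accrued in proportion to calls, which the documents neither state nor test, the 3-month contrast would shrink by about the same percentage. The arithmetic is certain; the size of any dilution is not, because visit timing is unknown.

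The effect is confined to the 3-month between-arm comparison of visit-based surveys (self-efficacy, social support, knowledge, quality of life, coping, communication) and to the mentee-only mentor ratings.

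Two stronger readings should be avoided. One is that the trial's main result is biased: the primary endpoint, the record-based secondary endpoints and the 12 to 18-month evaluation do not depend on this window. The other is that the arms have different windows: the schedule gives both the same one, and the asymmetry is only that controls have no calls left to receive.

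**What to change.** **Schedule.** In Section 1.3, open the Visit 2 window at the end of week 12 (day 84) in both arms and keep the close at month 3 plus 30 days. State the length of month 3 in days.

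**Analysis.** Flag Visit 2 surveys taken before day 84. Repeat the 3-month survey comparison without them in both arms, or with calls received before the visit, derived from billing-record dates. Label either version a sensitivity analysis: visit date and call count arise after randomization, and usual care participants have no mentor calls, so neither replaces the comparison of all randomized participants. Report the mentor ratings with the number completed before day 84.

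**Cost.** One schedule cell and one sensitivity analysis on data already collected. With month 3 as day 91, the window shrinks from 61 to 121 − 84 + 1 = 38 days, with some risk of more out-of-window visits. Phone, video and electronic surveys (Section 5.5) ease that. A later close would restore the width but measure further from the end of the calls, so it is not the first choice.

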## 6.3 MEASURES TO MINIMIZE BIAS: RANDOMIZATION AND BLINDING

We will randomize enrolled patient participants after completion of informed consent and the baseline visit utilizing a random number generator. As each subject is enrolled we will select envelopes with the random assignment to either the intervention or the usual care control group (1:1). The randomization will occur in blocks of between 28 to 42 depending upon the number of mentor and planned assigned mentees at the site. The goal is to have approximately equal total number of enrolled participants within each ~3-month intervention period. There may be staggering of the window and timeline depending upon enrollment pacing.

The mentee assignments will be blinded to usual care nephrologist and dialysis staff, but not to study subjects and mentors, because of the nature of intervention. The research team additionally will not be blinded to group assignment. While this may be preferred, it is not feasible in this pragmatic trial.

Enrolled participants will be encouraged to complete visit surveys on their own, to limit interactions with study staff in the process of data collection.

Trial randomization codes will be stored in a single file maintained by the data coordinating center. They will be shared with the research team as described above for patient participant assignment. Should accidental unblinding occur prior to completion of a baseline visit for a participant, the PI will be notified and this will be documented as a protocol deviation.

No change in study activities will occur in the event that it is identified that a usual care provider is unblinded to study assignment of their patient.

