#### 9.4.2 ANALYSIS OF THE PRIMARY ENDPOINT(S)

##### ED Visit and Hospitalization Count

Each month all enrolled patients will be evaluated for ED visit or hospitalization encounters by both self-report and medical record review. The events will be tabulated each month up to an 18-month period of follow-up. The rates of the composite event will be determined as event per patient-month and compared between the intervention and usual care group using Poisson regression with two random intercepts. In the regression model, the composite counts of ED visits and hospitalization during up to 18-months follow-up is the outcome variable and the intervention assignment of the mentees is the primary binary predictor. The log of follow-up time will be included as offset. The random intercepts will account for the correlation between mentees who share a common mentor as well as the correlation between mentees who are from a common dialysis facility (out of seven facilities). As a randomized controlled trial, we do not anticipate the need for covariate adjustment. However, if evaluation of patient characteristics by group identifies a failure of randomization and imbalance in key characteristics as an example including age, gender, comorbidity, race, or dialysis vintage they will be considered as adjustment variables in the analysis. We will control for type 1 error at 0.05. An exploratory analysis will consider the comparison between the groups but at 3-months of observation after the conclusion of the intervention delivery.

We will perform residual analysis for the mixed effects models. For mixed effects models, we will examine marginal residuals to check linearity and within-subjects covariance matrix and conditional residuals to check outliers as well as normality and homoscedasticity of the residual errors. In case Pearson residual analyses indicate overdispersion in the Poisson mixed effects model, we will perform quasi-Poisson model. We will use robust sandwich estimator in the presence of misspecification of the covariance matrix (i.e. random effects structure).

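### The primary count and its follow-up-time offset have no stated time zero, and the only start times given for patient participants differ by arm

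*Combined protocol and SAP*

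**What the plan says.** Section 1.3 (Schedule of Activities) closes with two start rules. For controls: "Usual care group start time will begin at the time they receive the study kidney disease educational materials". For the intervention arm: "Mentee group start time will begin at the time they receive their study phone and they are activated with their mentor". No maximum interval from randomisation to either event is given.

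Section 6.3 puts randomisation before activation: "We will randomize enrolled patient participants after completion of informed consent and the baseline visit utilizing a random number generator". It adds: "There may be staggering of the window and timeline depending upon enrollment pacing". Section 4.1 describes enrolment in groups until each mentor has a full allocation of mentees.

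Section 9.4.2 models the composite count of ED visits and hospitalisations over up to 18 months. On exposure time it says only: "The log of follow-up time will be included as offset". It does not say when that time begins. On ascertainment it says: "Each month all enrolled patients will be evaluated for ED visit or hospitalization encounters by both self-report and medical record review". The Schema text (Section 1.2) limits the data: "Medical record monthly review will only occur for the observation period and will also be truncated at the time of the T2 visit".

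Sections 6.4 and 9.3 commit the primary analysis to intention-to-treat, with non-participating mentees kept and all available data on randomised participants used. Section 7.2 lets a randomised person who does not receive the intervention be replaced, and does not repeat that this person remains in the analysis.

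**The concern.** Randomisation makes the arms comparable from the date of randomisation. If each arm's clock starts at its own later event, and the gap differs between arms, that protection is weakened.

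Three things follow if the Section 1.3 start times define the observation period. First, mentee admissions and ED visits between randomisation and activation fall outside the count. Second, the arms are followed over different stretches of time since enrolment. A log-time offset corrects for unequal length of follow-up, not for a different risk period. Third, a mentee who is never activated has no start date, so no follow-up time and no offset, and the intention-to-treat commitment cannot be carried out for that person as written.

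A changing early rate is plausible because an admission or an ED visit in the prior month is an entry route (Section 5.1). The checks in Sections 9.3 and 9.4.2 concern incomplete follow-up and missing values, and neither examines start dates. By Section 6.3, "The research team additionally will not be blinded to group assignment", so an origin left open would be settled by people who know the allocation.

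**Working it through.** **Inputs from the documents (Section 9.2).** Control rate 0.27 events per patient-month; 20% reduction (target rate ratio 0.80); 73 per group after drop-out, at least 100 per group recruited; type 1 error 0.05, two-sided by Section 9.4.1. The window was 18 months and is now 12, or 12 to 18 for people already enrolled (Section 1.1).

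**The plan's own power figure.** Poisson counts, no overdispersion or clustering, SE(log RR) = √(1/E0 + 1/E1). At 73 per group over 18 months:
- E0 = 73 × 18 × 0.27 = 354.8; E1 = 0.8 × 354.8 = 283.8; SE = 0.0796.
- |ln 0.8| / SE − 1.96 = 0.2231/0.0796 − 1.96 = 0.84, so power is 80.0%.

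The stated figure of more than 80% is therefore reproduced, to rounding, with 18 months per patient. The same formula at 12 months gives 62.9% (73 per group) or 76.4% (100 per group). That drop comes from the shorter window, not from the choice of origin.

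**Size of a shifted origin under no true effect.** The documents give neither a delay nor an early event rate, so everything in this step is assumed. Let the rate at t months after the control start, relative to steady state, be 1 + k·exp(−t/2). Here k is the average early excess (k = 1: every patient starts at twice the steady rate; k = 0.5: half of them do; k negative: early risk is lower). The mentee clock starts d months later and each arm is counted for 12 months.

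Null RR = ∫[d, d+12] / ∫[0, 12], where ∫[a, b] = (b − a) + 2k·(e^(−a/2) − e^(−b/2)).

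Worked case, k = 0.5, d = 1: numerator 12.605, denominator 12.998, RR = 0.970.

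| k | d = 0.5 | d = 1 | d = 2 |
|---|---|---|---|
| 0 (constant rate) | 1.00 | 1.00 | 1.00 |
| 0.25 | 0.99 | 0.98 | 0.97 |
| 0.5 | 0.98 | 0.97 | 0.95 |
| 1 | 0.97 | 0.94 | 0.91 |

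For d = 1, k = −0.3 gives 1.02 and k = −0.5 gives 1.04. If mentee counting instead ends 12 months after the control start, the d = 1 row for k = 0.25, 0.5 and 1 reads 0.99, 0.97 and 0.95.

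The shape also matters. If the rate is exactly doubled for month 1 only and d = 1, the control window holds 13 units and the mentee window 12, so RR = 12/13 = 0.92.

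**Power cost of a randomisation clock.** Suppose the 20% effect begins only at activation, d months after randomisation. Then E0 = 0.27·T·n and E1 = 0.27·n·(d + 0.8(T − d)). For n = 100, T = 12, d = 1:
- E0 = 324.0; E1 = 27 × (1 + 8.8) = 264.6; RR = 0.817; SE = 0.0829.
- 0.2025/0.0829 − 1.96 = 0.48, so power is 68.6%.

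| n per group, months | no lag | 0.5 month | 1 month | 2 months |
|---|---|---|---|---|
| 100, 12 | 76% | 73% | 69% | 60% |
| 100, 18 | 91% | 89% | 87% | 83% |

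**The case against.** The strongest reply is that the Section 1.3 sentences only schedule visits. They sit under a visit table, and the parallel sentence for mentors says outright that its start date fixes when later study visits fall. Section 9.4.2 never links the offset to these dates. Section 9.4.3 models the monthly secondary endpoints by months from baseline, and those come from the same monthly chart review (Section 8.1) as the primary events. Section 8.3.4 records adverse events from consent. This reading is plausible. It still leaves the primary count without a common origin. Moreover, record review stops at the T2 visit, so whatever clock schedules T2 also sets where the count ends.

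The control clock may also start after randomisation. In Section 6.1.1 the mentee pack contains one appendix document that the control pack lacks, so a complete pack cannot be chosen before allocation. What counts is the difference in lag between arms, which could be small. That stands.

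Two stronger readings are tempting and are not supported. One is that replaced non-starters are dropped from the analysis. Sections 6.4 and 9.3 keep all randomised participants, and nothing removes those who are replaced; what is missing is a sentence in Section 7.2 saying so. The other is that mentees using their own phone, as Section 6.1.1 permits, have no start date. Mentor activation still gives them one.

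**Conclusion.** The point stands as a gap in the definition of the primary analysis. The only stated start events differ by arm, Section 9.4.2 supplies no other origin, and if those events define observation the plan leaves out mentee events before activation and gives a never-activated mentee no follow-up time.

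A reader might infer that the result is biased in favour of mentoring. The documents do not support that. No delay is recorded; group enrolment and staggering only allow one. With a constant rate the bias is zero. Only two of the eight qualifying routes in Section 5.1 are recent acute events, and the direction reverses if early risk is lower. The range of 0.94 to 1.04 for a 1-month lag is an illustration under an assumed decay, not an estimate, and a different assumed shape gave 0.92. Against a target of 0.80, shifts of this order are enough to justify settling the origin before analysis.

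How counting ends for people discontinued under Section 7.2 is a separate censoring question and forms no part of this point.

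**What to change.** In Section 9.4.2, define the primary count and the offset as starting on the date of randomisation in both arms, and abstract records from that date. Count the limit on observation from the same date, so that the arm difference does not reappear at T2. State in Section 1.3 that activation is used only to schedule calls and surveys.

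In Section 7.2 or 9.3, add that randomised participants who are replaced stay in the intention-to-treat set, in their assigned arm, from randomisation. Report the randomisation-to-start interval by arm, and keep the activation-based clock as a sensitivity analysis.

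The cost is wording, chart review for the weeks before activation, and the power loss tabulated above, which arises because unexposed mentee time is counted. Those power figures ignore overdispersion and clustering, so they are optimistic in level. Keeping the interval from randomisation to activation short limits the loss.
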